Weight/Efficacy Tildacerfont Dose Adjustment	X		X	X	X	X	X	X	X			
Dispense study drug	X	X	X	X	X	X	X	X	X			
Review any AEs	X	X	X	X	X	X	X	X	X	X	X	X
Study drug accountability	X	X	X	X	X	X	X	X	X	X	X	

Abbreviations: 11KT=11-ketotestosterone; A4=androstenedione; ACTH=adrenocorticotropin hormone; AEs=adverse events; ALT=alanine aminotransferase; ALP=alkaline phosphatase; AST=aspartate aminotransferase; C-SSRS=Columbia–Suicide Severity Rating Scale; ECG=electrocardiogram; EOT= end of treatment; ET=early termination; FOCP=female of childbearing potential; GC=glucocorticoid; GGT=gamma-glutamyl transferase; PD=pharmacodynamics; PROMIS= Patient Reported Outcomes Measurement Information System; 17-OHP=17-hydroxyprogesterone; SWYC=Survey of Well-being of Young Children; T=testosterone.

¹ A serum pregnancy test will be performed at Screening for FOCP only. All subsequent tests will be urine pregnancy tests

² Labs will be drawn at 8 AM (±1 h) before any morning dose of GC medication.

³ Laboratory assessments include: hematology, chemistry (including liver function tests AST, ALT, ALP, GGT, total and direct bilirubin, and total bile acids), thyroid panel. Fasting is not required.

⁴ As needed based upon any safety concerns, per Investigator discretion.

⁵ PD Samples (ACTH, 17-OHP, A4, testosterone, and 11KT). They must be drawn prior to GC dosing. Fasting is not required. Single samples for plasma concentration of tildacerfont will be drawn at all visits.

⁶ GC dose (frequency or total daily dose) may be adjusted based on A4 levels collected at each visit. If a change in GC is warranted by the A4 algorithm, sites will contact participants by telephone after receipt of results (within approximately 2 weeks) after each applicable study visit.

⁷ Urinalysis should include the following: specific gravity, pH, glucose, protein, blood, ketones, bilirubin, urobilinogen, nitrite, by dipstick. Microscopic examination should be obtained if blood or protein is abnormal.

⁸ Systolic and diastolic blood pressure, pulse rate, body temperature, and respiration rate.

⁹ The C-SSRS, to assess suicidality, is only conducted for participants aged ≥6 years.

¹⁰ PROMIS, to assess anxiety and depression, is conducted for participants aged ≥5 years.

¹¹ The SWYC to assess anxiety and depression is only conducted in Cohort 7 (and 9 if indicated) for participants ≤5 years of age.

¹² Historical bone age and predicted adult height calculation will be performed by an x-ray of left hand and wrist to assess bone age and calculate predicted adult height. This may not be performed if deemed inappropriate by the investigator (based on maturation level). This will not be performed in adults (Cohorts 4 & 5).

CONFIDENTIAL

Page 85 of 87

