3.1.2.6. Visit 6 (EOT for Cohorts 1-3) (Week 12 ±3 days)

Visit 6 will be conducted as an outpatient visit. The following activities will be performed:

- Review concomitant medications for any changes
- Pregnancy test for FOCP (urine)
- Safety labs (see [Appendix 1](#))
- Pharmacodynamics (ACTH, 17-OHP, A4, testosterone, and 11KT) drawn prior to GC dosing at approximately 8 AM (±1 hour). Fasting is not required.
- Cortisol
- Tildacerfont concentration (single sample) drawn prior to GC dosing at approximately 8 AM (±1 hour). Fasting is not required.
- GC dosing adjustments (for Cohort 1-3 patients who are continuing in the EP) to be determined after A4 value is resulted
- Urinalysis
- Vital signs: blood pressure, pulse rate, body temperature, respiration rate, and weight
- Physical exam (full)

- 12-lead ECG
- Suicidality Questionnaire- C-SSRS since last visit (participants aged 6- to 17-years only)
- Depression and Anxiety Questionnaires (PROMIS or SWYC depending on age of participant)
- Study drug accountability
- Assess for AEs

3.1.2.7. Safety Follow-up Visit Telephone Call (30 days after last dose \pm 7 days)

Approximately 30 days after the last dose of study drug (post the 12- or 4-week treatment period, depending on cohort, or post the extension), participants will have a final follow-up visit conducted by telephone. Concomitant medications and AEs will be reviewed. If any ongoing safety issues are identified, the participant may be asked to visit the clinic for additional tests, labs, or assessments.

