3.1.3. Extension Period

Participants who complete the 12- or 4-week treatment period, depending on cohort, may be eligible to continue dosing to complete 2 years on treatment in an extension study. Participants will sign a separate informed consent form at Week 12 or Week 4. Pending DMC review, participants in Cohorts 1 and 1a (if indicated) will receive the adult equivalent dose of 200 mg QD during the extension (i.e., Cohort 1 participants will immediately switch to 200 mg equivalent if the DMC has already recommended this dose for Cohort 2, or participants may enter the extension period on 50 mg equivalent and increase to 200 mg equivalent after such a recommendation is made). If a Cohort 1-3 participant is to dose escalate to the 200 mg equivalent, they may do so at the next scheduled visit or come to the clinic for an unscheduled visit and pick up their new supply of study drug. Participants will receive a follow-up phone call 2 weeks after dose escalation to check for AEs.

Further tildacerfont dose adjustments may occur during the extension on a case-by-case basis at the discretion of the Investigator with Sponsor approval. Any extension participant may receive the highest dose recommended by the DMC for their age group. Dose changes (increase or decrease) may occur at a scheduled visit, an unscheduled visit, or via a phone visit, but any dose escalation > 200mg QD will be followed by safety labs (link to list) within 2-4 weeks of the change. Once all participants are in the extension period, safety- data will be reviewed every 6 months by the DMC. Weight-based dose adjustments may be made at any extension visit, with no follow-up labs required.

For Cohorts 1-3, the first visit of the extension will be Week 12. For Cohorts 4-9, Week 4 will be the first extension visit, followed by extension clinic visits at Weeks 8 and 12 (\pm 2 weeks). Starting at Week 12, all participants will attend clinic visits every 12 weeks (\pm 2 weeks).

Approximately a 12-week supply of study drug, as appropriate, will be dispensed at each visit. Approximately 30 days after the last dose of study drug, participants will have a final follow-up visit conducted by telephone. Concomitant medications and AEs will be reviewed. If any ongoing safety issues are identified, the participant may be asked to visit the clinic for additional tests, labs, or assessments.

The extension study visits will include the following:

- Review concomitant medications for any changes

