- Physical exam (abbreviated/directed)
- Vital signs: blood pressure, pulse rate, body temperature, respiration rate, and weight
- Safety labs (see [Appendix 2](#) and [Appendix 4](#))
- Pregnancy test for FOCP (urine)
- Urinalysis (Weeks 48 and 96 only)
- Pharmacodynamics (ACTH, 17-OHP, A4, testosterone, and 11KT) drawn prior to GC dosing at approximately 8 AM (\pm 1 hour). Fasting is not required.
- Tildacerfont concentration (single sample)

SPR001-205
Spruce Biosciences, Inc.

CLINICAL STUDY PROTOCOL
Version 5.0

- Study drug accountability
- Suicidality Questionnaire- C-SSRS since last visit (participants aged ≥ 6 years only)
- Depression and Anxiety Questionnaires (PROMIS or SWYC depending on age of participant)
- GC dosing adjustments
- Assess for AEs
- Bone age and predicted adult height calculated from X-ray image of left hand and wrist (every 6 months if deemed appropriate by Investigator, see [Appendix 2](#) and [Appendix 4](#)).
- Tildacerfont dose adjustment as needed (based on recommendation of investigator or due to weight-based dosing changes)

4. STUDY POPULATION**4.1. Eligibility Criteria****4.1.1. Inclusion Criteria**

A participant must meet all of the following criteria to be eligible for this study:

1. Male and female participants aged 2- to 10-years (Cohorts 3, 7, and 9), 11- to -17 years (Cohorts 1, 1a, 2, 6, and 8), and ≥ 18 years (Cohorts 4 and 5) at Screening.
2. For participants aged 2 to 5 years, a minimum weight at Screening of 11 kg.
3. Has a known childhood diagnosis of classic CAH due to 21-hydroxylase deficiency (21-OHD) based on genetic mutation in CYP21A2 and/or documented (at any time) elevated 17-OHP and currently treated with hydrocortisone (HC), HC acetate, prednisone, prednisolone, methylprednisolone (or a combination of these). Other types of CAH may be allowed with Sponsor approval.
4. For participants in Cohorts 4-9, $1.2X \text{ ULN} < A4 < 4X \text{ ULN}$. A4 values outside of this range may be allowed with Medical Monitor (MM) approval.
5. A stable dose of GC replacement for ≥ 1 month before Screening without evidence of non-adherence (as assessed by Investigator). Weight-based dose adjustments or stress dosing in the month prior to Screening are not exclusionary but should be discussed with the MM.
6. For participants on mineralocorticoid replacement, a stable dose for ≥ 1 month prior to Screening.

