6.1.5. Suicidality Stopping Criteria

Tildacerfont is a central nervous system (CNS)-active drug. Some CNS-active drugs may be associated with an increased risk of suicidal ideation in certain populations. Although tildacerfont has not been shown to be associated with an increased risk of suicidal thinking or behavior in past clinical studies, participants will be monitored for such events during this study using the C-SSRS. Any participant who exhibits Suicidal Behavior or Suicidal Ideation in their responses on the C-SSRS, will have study drug immediately discontinued and should be evaluated by a psychiatrist. This safety finding will be considered an AESI if it is not an SAE (e.g., requiring hospitalization) (see [Section 7.2.8](#)).

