7.2.8. Adverse Events of Special Interest

AESIs are those AEs (independent of seriousness criteria) that are of specific concern to this study and for which ongoing monitoring and communication with the Investigator and Sponsor may be appropriate. These events will be reported on the SAE Report Form, allowing for the collection of additional information, as warranted. The following may be considered AESIs for this study:

- Significant liver chemistry changes that do not satisfy study drug stopping rules (see [Section 6.1.2](#)). Cases of Hy's Law should be reported as an AESI and SAE.
- Suicidality as indicated by responses on the C-SSRS (see [Section 6.1.5](#) regarding study stopping criteria).
- Depression or anxiety that is moderate or severe (CTCAE Grade 2 or higher), as assessed by the Investigator (see [Section 6.1.6](#) regarding study drug stopping criteria for depression or anxiety). This will be reported as an AESI and if seriousness criteria are met, reported as an SAE.
- Adverse events of adrenal insufficiency are considered AESIs and will be reported on a separate Adrenal Insufficiency Form. Additionally, symptoms of adrenal insufficiency will be reported as SAE if they necessitate parenteral GC administration by a health care professional and two of the following criteria occur or are met: hypotension (systolic blood pressure <90 mmHg); nausea or vomiting; severe fatigue; documented hyponatremia, hyperkalemia, or hypoglycemia. If hospitalization was required or the event of adrenal insufficiency is deemed to be an important medical event, life-threatening, or results in a persistent or significant disability/incapacity or death, it should also be reported as an SAE.
 - For SAEs of adrenal insufficiency, records from the office of the health care provider, emergency facility or hospital should be obtained as source documents to provide the following information:
 - Was stress dosing employed prior to the adrenal insufficiency event? If yes, what were the GC dose and duration of dosing and the cause for stress dosing prior to seeking medical attention?
 - What type, dose and route of parenteral GC was administered and the duration of administration?
 - What concomitant medications were administered?
 - What clinical laboratory results are available?
 - What AEs occurred?
 - What was the duration of stay if admitted to the hospital?
 - What was deemed to be the inciting factor leading to adrenal crisis?

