³ Laboratory assessments include: hematology, chemistry (including liver function tests AST, ALT, ALP, GGT, total and direct bilirubin, and total bile acids), thyroid panel. Fasting is not required.

⁴ As needed based upon any safety concerns, per Investigator discretion.

⁵ PD Samples (ACTH, 17-OHP, A4, testosterone, and 11KT). They must be drawn prior to GC dosing. Fasting is not required. Single samples for plasma concentration of tildacerfont will be drawn at all visits.

⁶ GC dose (frequency or total daily dose) may be adjusted based on A4 levels collected at each visit. If a change in GC is warranted by the A4 algorithm, sites will contact participants by telephone after receipt of results (within approximately 2 weeks) after each applicable study visit.

⁷ Urinalysis should include the following: specific gravity, pH, glucose, protein, blood, ketones, bilirubin, urobilinogen, nitrite, by dipstick. Microscopic examination should be obtained if blood or protein is abnormal.

⁸ Systolic and diastolic blood pressure, pulse rate, body temperature, and respiration rate.

⁹ The C-SSRS, to assess suicidality, is only conducted for participants aged 6 to 17 years.

¹⁰ PROMIS, to assess anxiety and depression, is conducted for participants aged 5 to 17 years.

¹¹ The SWYC to assess anxiety and depression is only conducted in Cohort 3 participants under 5 years of age.

¹² Historical bone age and predicted adult height calculation will be performed by an x-ray of left hand and wrist to assess bone age and calculate predicted adult height.

SPR001-205

Spruce Biosciences, Inc.

CLINICAL STUDY PROTOCOL

Version 5.0

APPENDIX 3. SCHEDULE OF ACTIVITIES FOR COHORTS 4, 5, 6, 8, 7, and 9

	Screening ¹	Treatment Period			Early Termination	Safety Follow-up ²
		Day 1	Week 2	Week 4 (EOT)		
VISIT NUMBER	1	2	3	4		5
STUDY DAY	≤14 days before V2	1	14	28		Last dose +30 days
Visit windows			+3 days	±3 days		± 7 days
Informed consent/assent	X					
Inclusion/exclusion criteria	X	X				
Demography & medical history	X					
Review of prior medications from past year	X					
Review of concomitant medications	X	X	X	X	X	X
Hepatitis B & C and HIV Screening	X					
Pregnancy test for FOCP ³	X	X	X	X	X	X ⁶
Laboratory assessments ^{4, 5}	X	X	X	X	X	X ⁶
Pharmacodynamics and Tildacerfont Concentration Samples (by Cohort)						
Cohorts 4, 5, 6, and 7 PD markers and tildacerfont concentration (serial, drawn together) ⁷ (also 8 and 9 if indicated)		X	X			

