#### *5.3.1.7 Psychiatric Evaluations*

Subjects will be monitored for depression and anxiety during the study using the Patient Reported Outcomes Measurement Information System (PROMIS) Pediatric SF (Short Form) v2.0, the PROMIS Parent-Proxy SF (Short Form) v2.0, or the Survey of Well-Being of Young Children (SWYC). The questionnaire used will depend upon the subject's age. Any subject who

develops severe depression or anxiety (CTCAE Grade 3 or higher), as assessed by the Investigator, will require study drug discontinuation and appropriate follow-up. The Columbia–Suicide Severity Rating Scale will be used during the study to monitor suicidal ideation and behavior for subjects aged 6 to 17 years old. The Baseline/Screening Version of the C-SSRS, which assesses both lifetime history and history from the last 12 months, will be used at the Screening Visit to determine subject eligibility. The Since Last Visit Version of the C-SSRS will be used at all subsequent visits (Week 2, Week 4, Week 8, and Week 12) as specified in [Table 8](#), [Table 9](#), [Table 10](#), and [Table 11](#).

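### For Cohorts 1-3 the protocol gives two age ranges for the C-SSRS (6 to 17, and 6 and over), and one of them could end scheduled assessment when a participant turns 18 on drug

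*Protocol*

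**What the plan says.** Two age ranges are in force for Cohorts 1-3.

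**Upper limit of 17.** Appendix 1 footnote 16 (treatment period) and Appendix 2 footnote 9 (extension), both written for Cohorts 1, 1a, 2 and 3, state: "The C-SSRS, to assess suicidality, is only conducted for participants aged 6 to 17 years". Protocol Section 3.1.2.5 (Week 8) and Section 3.1.2.6 (Week 12) agree; the latter lists "C-SSRS since last visit (participants aged 6- to 17-years only". SAP Section 5.3.1.7 says the scale is used "to monitor suicidal ideation and behavior for subjects aged 6 to 17 years old", and the footnotes to SAP Tables 8 and 9 repeat the limit.

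**No upper limit.** Section 3.1.3, which lists the activities at extension visits without restricting them by cohort, has "C-SSRS since last visit (participants aged ≥ 6 years only". Sections 3.1.2.3 (Week 2), 3.1.2.4 (Week 4) and 3.1.2.8 (Early Termination) use the same lower limit alone. The schedules for Cohorts 4-9 (Appendices 3 and 4) also read "The C-SSRS, to assess suicidality, is only conducted for participants aged ≥6 years", but they do not govern Cohorts 1-3.

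Section 3.1.3 covers Cohorts 1-3 expressly: "For Cohorts 1-3, the first visit of the extension will be Week 12".

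Section 6.1.5 makes the C-SSRS the trigger for a mandatory stop, with no age limit: "Any participant who exhibits Suicidal Behavior or Suicidal Ideation in their responses on the C-SSRS, will have study drug immediately discontinued". Section 7.2.8 defines one of the adverse events of special interest as "Suicidality as indicated by responses on the C-SSRS".

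**The concern.** Participants in Cohorts 1, 1a and 2 enter at 11 to 17 years and may be treated for up to two years (Section 3.1.3), so some could turn 18 while on drug. A coordinator working from the Appendix 2 grid would find an instruction that, read by current age, ends the scale at that birthday. A coordinator working from Section 3.1.3 would continue it. Nothing in either document says which text prevails.

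At stake is scheduled detection of suicidality. Section 6.1.5 describes the drug as active in the central nervous system and commits to C-SSRS monitoring during the study. The mandatory stop and the special-interest event both depend on C-SSRS responses. If the scale is no longer scheduled for a participant, neither can be triggered by a routine assessment.

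**Working it through.** The plan states no figure on this point. The check is a comparison of text, followed by simple arithmetic on who could be exposed.

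**Step 1. C-SSRS age statements that apply to Cohorts 1-3 after Screening**

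| Place in Protocol | Visit | Age range |
|---|---|---|
| 3.1.2.3 | Week 2 | 6 and over |
| 3.1.2.4 | Week 4 | 6 and over |
| 3.1.2.5 | Week 8 | 6 to 17 |
| 3.1.2.6 | Week 12 | 6 to 17 |
| 3.1.2.8 | Early Termination | 6 and over |
| 3.1.3 | Extension, starting at Week 12 | 6 and over |
| Appendix 1, fn 16 | Treatment period | 6 to 17 |
| Appendix 2, fn 9 | Extension | 6 to 17 |

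Week 12 appears under both rules. Every extension visit also has one rule in the body text and another in the appendix.

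**Step 2. Which age?** None of these lines says whether age is current or taken at Screening. Two other uses of age in the protocol are tied to Screening: eligibility (Section 4.1.1, criterion 1) and the dose table (Section 5.1).

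**Step 3. Who could turn 18 on drug?** The age on Day 1 at which a participant reaches 18 by week *w* is 18 − 7*w*/365.25.

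- Week 12: 84/365.25 = 0.230 years; 18 − 0.230 = 17.77 years.
- Week 96 (last scheduled extension visit): 672/365.25 = 1.840 years; 18 − 1.840 = 16.16 years.

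Those exposed during scheduled treatment are therefore about 16.2 years or older on Day 1. The double rule at Week 12 itself matters only for those aged about 17.8 or older. Cohort 3 enters under 11 and is under 13 at Week 96 (11 + 1.84 = 12.84), so it cannot be affected.

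**Step 4. How many assessments?** After Week 12, Appendix 2 schedules Weeks 24, 36, 48, 60, 72, 84 and 96, which is seven visits. A participant who turns 18 between Week 12 and Week 96 would miss between one and seven, depending on the birthday.

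**Step 5. Illustrative share.** Assume entry ages uniform over 11 to under 18 (a 7-year span) and full retention to Week 96. Neither assumption comes from the documents.

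- Turning 18 between Day 1 and Week 96: 1.840/7 = 0.263.
- Turning 18 between Week 12 and Week 96: (1.840 − 0.230)/7 = 1.610/7 = 0.230.
- If only half enter the extension: 0.115 to 0.131.

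These are shares of the adolescents in Cohorts 1, 1a and 2.

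**The case against.** The best defence is that this is uneven drafting and that no cut-off at 18 was meant. The range with an upper limit appears in protocol text written only for Cohorts 1-3, which enrol no one over 17. The range without one appears in text shared with Cohorts 4-9, which include adults, and in those cohorts' own schedules. On this view 17 simply restates the top enrolment age, and the working restriction is the floor of 6. Because eligibility and dosing both use age at Screening, a site could reasonably read the footnote the same way, and then nobody ages out. Section 6.1.5 sets no upper age, Section 7.1.6 allows questionnaires as needed, and adverse events are reviewed at every visit.

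Much of this stands. The entry-age reading is plausible, and nothing shows an intention to stop at 18. It does not remove the conflict, because the footnote's literal words permit the other reading and Section 3.1.3 applies to the same participants without the limit.

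Three stronger readings are tempting, and the documents do not support them.

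- *The suicidality stopping rule is disabled for those who turn 18.* It is not. As-needed questionnaires, adverse event review and the Investigator's general right to stop drug (Section 6.1) remain.
- *Some three to five participants are affected.* Section 1.2.3 reports 30 pediatric participants in Cohorts 1-3. Applying the planned adolescent share gives 30 × 10/20 = 15 to 30 × 15/25 = 18, and then 15 × 0.230 = 3.5 to 18 × 0.263 = 4.7. But no age split is given, 30 already exceeds the planned maximum of 25, and the uniform-age and full-retention assumptions are untested.
- *PROMIS should be opened to adults in the same edit.* Its footnotes have a similar ceiling, but Sections 7.1.6.2 and 7.1.6.3 name only Pediatric and Parent Proxy forms, whose suitability above 17 the documents do not address.

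**Conclusion.** The inconsistency is real, and no text in either document resolves it. Its consequence is conditional: a site must follow Appendix 2 over Section 3.1.3, read the range as current age, and have a Cohort 1, 1a or 2 participant aged about 16.2 or more on Day 1 who continues in the extension. How often that happens is unknown and may be never. Where it does, scheduled suicidality assessment would lapse while drug continues, with the other safeguards still in place. Confidence is high for the wording conflict and low for the number of participants. It should be corrected, because the instrument triggers a mandatory stop and sites should not have to choose between two rules for it.

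**What to change.** Change Appendix 2 footnote 9, Appendix 1 footnote 16 and Sections 3.1.2.5 and 3.1.2.6 to 6 years and over, matching Section 3.1.3. Align SAP Section 5.3.1.7 and the footnotes to SAP Tables 8 and 9. The SAP edits are for consistency only: psychiatric assessments are listed and not summarised (SAP Section 14.5), and SAP Section 4 assigns the extension analysis to a separate SAP.

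The cost is a few words and, for any participant who turns 18, one questionnaire at visits that already take place.

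Treat the PROMIS age limit as a separate change, to be made only together with a form suited to participants aged 18 and over.
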